5.4 ClinicalTrials.gov Outcomes

Similar to endpoints, ClinicalTrials.gov outcomes are assessments that evaluate the Roadmap to Parenthood intervention. Following are the ClinicalTrials.gov outcome titles; descriptions, and timeframes.

Outcome 1 (Primary)

Title: Decisional Conflict Scale (DCS)

Description: The Decisional Conflict Scale (DCS) is a validated survey that assesses personal uncertainty in making healthcare decisions; modifiable factors contributing to uncertainty; and the quality of the decision made. It is reliable and responsive to change, and the most widely used measure of decision-making quality. The survey has 16 questions, with responses on a 5-point scale ranging from “strongly agree” (1) to “strongly disagree” (5). Total scores range from 16 to 80, with higher scores indicating greater uncertainty (worse outcome). The outcome will be reported as the mean difference from baseline to 1 and 3 months, with standard deviation.

Timeframe: 3 months

Outcome 2 (Secondary)

Title: Unmet Fertility Information

Description: This investigator-designed survey assesses perceived information needs about fertility topics such as the risk of infertility; risk of early menopause; options to assess fertility status; options to preserve fertility; and options for alternative family-building. The survey has 5 questions, each answered by a Yes / No response. Yes is scored as 1, and no is scored as 0. Total scores range from 0 to 5, with higher scores indicating greater perceived knowledge. The outcome will be reported as the mean difference from baseline to 1 and 3 months, with standard deviation.

Timeframe: 3 months

Outcome 3 (Secondary)

Title: Illness Perceptions Questionnaire-Revised (IPQ-R)

Description: The Illness Perceptions Questionnaire-Revised (IPQ-R) is a survey that assesses cognitive and emotional representations of illness and is validated in cancer populations. The survey has 28 questions, answered on a 5-point scale ranging from “strongly disagree” (1) to “strongly agree” (5). Total scores range from 28 to 140, with higher scores indicating worse outcomes. The outcome will be reported as the mean difference from baseline to 1 and 3 months, with standard deviation.

Timeframe: 3 months

Outcome 4 (Secondary)

Title: Reproductive Concerns After Cancer (RCAC) Scale

Description: The Reproductive Concerns After Cancer (RCAC) Scale is a validated survey of cancer survivors’ fertility and health concerns. The survey has 18 questions, answered on a 5-point scale ranging from (1) “strongly disagree” to (5) “strongly agree.”

Total scores range from 18 to 90, with higher scores indicating greater distress (worse outcome). The outcome will be reported as the mean difference from baseline to 1 and 3 months, with standard deviation.

Timeframe: 3 months

Outcome 5 (Secondary)

Title: Impact of Events Scale-Revised (IES-R)

Description: Impact of Events Scale-Revised (IES-R) is a validated measure of distress in reaction to negative life events that has been adapted to measure current subjective distress related to infertility risk. The survey has 15 questions, intended to collect the participant's assessment of intrusive thoughts (7 questions) and effortful avoidance of reminders about a distressing event (8 questions). The questions are answered on a 5-point scale ranging from "not at all" (1) to "extremely" (5). Total scores range from 15 to 75, with higher scores indicating greater distress (worse outcome). The outcome will be reported as the mean difference from baseline to 1 and 3 months, with standard deviation.

Timeframe: 3 months

Outcome 6 (Secondary)

Title: PROMIS Self-Efficacy (PROMIS-SE)

Description: The PROMIS General Self-Efficacy and Self-Efficacy for Managing Emotions subscales measure the degree to which people feel confident in managing various situations, problems, and events and confidence in managing difficult emotions. Questions will assess general self-efficacy in these domains and self-efficacy in managing fertility and family-building issues and emotions. The survey has 16 questions, intended to collect the participant's assessment of general self-efficacy (4 items), self-efficacy for managing fertility/family-building issues (4 items), self-efficacy for managing difficult emotions (4 items), and self-efficacy for managing difficult emotions related to fertility/family-building (4 items). The questions are answered on a 5-point scale ranging from (1) "I am not at all confident" to (5) "I am very confident." The outcome will be reported as the mean difference from baseline to 1 and 3 months, with standard deviation.

Timeframe: 3 months

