The study intervention is the Roadmap to Parenthood decision aid and planning tool (previously developed) addresses the maladaptive cognitive-emotional and behavioral responses YA-Fs' may have adopted to manage uncertainty and distress, and offer alternative planning strategies to support decision making, address barriers, and build hope that parenthood is possible. The Roadmap to Parenthood is an interactive website intended to improve decision-making regarding family-building after cancer. Effectiveness (efficacy) of Roadmap to Parenthood is measured by a number of questionnaires (surveys), also web-based. Representations of these data collection surveys are provided as appendices to this protocol document.

Summary of the premise of the study. YA-Fs report a lack of knowledge coupled with high levels of distress about their fertility and are in need of continued decision and planning support to achieve their desired family-building goals. To address this gap, the proposed study will pilot test the first theoretically driven, evidence-based decision aid and planning tool for family-building after cancer. We hypothesize the web-based tool will help YA-Fs become informed, manage negative affect, and plan financially for future costs, thereby addressing key barriers to family-building after cancer, while inspiring hope that parenthood will be achieved. Young adult cancer survivors are an underserved patient group characterized by disparities in service delivery and outcomes.²² Developing an intervention to support post-treatment family-building will fill a critical unmet service need in AYA survivorship care.

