4.0 MATERIAL AND METHODS

We conduct a single-arm pilot study of the Roadmap to Parenthood decision aid intervention for family-building after cancer. The Roadmap to Parenthood consists of an online decision aid tool that provides information, support, and guidance to YA-F cancer survivors making decisions about fertility and family-building options after cancer. The decision aid intervention will be presented as a webpage accessed via www.familybuildingaftercancer.com. The Roadmap to Parenthood website is a multi-page interactive resource that provides information, resources, and potential questions a participant might use to gather more information about family-building. The decision aid intervention is intended to help women investigate their options to have a child after cancer treatment and make decisions relative to their condition that are aligned with their family-building goals.

Separate from the Roadmap to Parenthood tool, participants will be asked to complete psychosocial assessment questionnaires (table of contents to the questionnaires in Appendix B) to track decisional conflict (Appendix F, the primary outcome) and cognitive-emotional and behavioral functioning (collectively, the secondary outcomes in subsequent appendices), as well as a priori covariates and process variables including sociodemographic and medical characteristics, uncertainty management preference, financial well-being, and health literacy. The questionnaires

are all quantitative assessments used to assess effectiveness of the Roadmap to Parenthood intervention and include:

- Decisional Conflict Scale (DCS), Appendix F: 16-item measure, answered on a 5-point scale ranging from “strongly agree” to “strongly disagree” with higher scores indicating greater uncertainty (worse outcome).
- Unmet Fertility Information Needs, Appendix G: 5-item measure, answered with yes/no response options with higher scores indicating better perceived knowledge (better outcome).
- Illness Perceptions Questionnaire-Revised (IPQ-R), Appendix H: 28 items, answered on a 5-point scale ranging from “strongly disagree” to “strongly agree” with higher scores indicating worse outcomes.
- Reproductive Concerns After Cancer (RCAC) Scale, Appendix I: 8-item measure, answered on a 5-point scale from “strongly disagree” to “strongly agree” with higher scores indicating greater distress (worse outcome).

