Illness Perceptions Questionnaire-Revised (Appendix H): ²⁴ Validated measure of cognitive and emotional representations of illness. Items were adapted to refer to participants' infertility risk. 5 subscales will be used (5 to 6 items each; 28 items total): Personal control, Treatment control, Illness coherence, Consequences, and Emotional representations. Items are answered on a 5-point scale from "Strongly Agree" to "Strongly Disagree," with higher scores indicating worse outcomes. Each subscale is scored separately, and averages are calculated. The IPQ-R has been validated in cancer populations.	X	X	X
Reproductive Concerns after Cancer Scale (Appendix I): ²⁵ Validated, 18-item measure of AYA-F cancer survivors' fertility and health concerns with 6 subscales: Concerns about fertility potential, Partner disclosure, Becoming pregnant, Child's health, Personal health, and Acceptance. Answers are on a 5-point scale, "Strongly Disagree" to "Strongly Agree" with higher scores indicating more concern (worse outcome). Mean scores are calculated, ranging from 1 to 5.	X	X	X
Impact of Events Scale-Revised (Appendix J): ²⁶ The IES-R is a validated measure of distress in reaction to negative life events and will be adapted to measure current subjective distress related to infertility risk. The Intrusive Thoughts (7 items) and Avoidance (8 items) subscales assess intrusive thoughts and effortful avoidance of reminders about a distressing event, respectively. Answers are on a 5-point scale: "Not at all" to "Extremely."	X	X	X
PROMIS Self-Efficacy (Appendix K): ²⁷ The PROMIS General Self-Efficacy and Self-Efficacy for Managing Emotions subscales measure the degree to which people feel confident in managing various situations, problems, and events and confidence in managing difficult emotions. Questions will assess general self-efficacy in these domains and self-efficacy in managing fertility and family-building issues and emotions.	X	X	X

	Timepoint		
	T1: baseline; pre-intervention	T2: 1-month post-baseline	T3: 3-months post-baseline

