For **Study Objective 2**, for each outcome variable, we will examine the distributional qualities, extent of missing data, and satisfaction of assumptions of randomness (ie, MAR, MCAR). Descriptive statistics will evaluate sample characteristics. Covariates with significant relationships with the decisional conflict scale (DCS) will be included in final models. To obtain an effect size estimate of the decision aid in reducing decisional conflict, pairwise t-test will evaluate change in DCS mean scores from T1 to T2. A two-sided hypothesis test of the within-subject difference in adjusted means will test the null hypothesis ($H_0: \mu_1 = \mu_2$) at $\alpha = 0.05$. Rejection of the null hypothesis will indicate a significant within-subject DCS mean change from T1 to T2 ($H_1: \mu_1 > \mu_2$). Effect size estimates (Cohen’s d) will be calculated and reported. On an exploratory level, we will examine T1 to T3 and T2 to T3 mean differences to characterize the DCS trajectory. Similar procedures will analyze changes in the IPQ-R, RCACS, PROMIS Self-Efficacy, and the IES-R as secondary outcomes, controlling for key covariates. The Stage of Decision Making Scale will be assessed, and descriptive statistics will evaluate whether use of the decision aid website impacts readiness to engage in decision making, progress in making a choice, and receptivity to considering or re-considering options between timepoints T1 and T2 and between timepoints T2 and T3. The Preparation for Decision Making Scale will be assessed, and descriptive statistics will evaluate whether use of the decision aid website impacts perception of how useful a decision aid or other decision support intervention is in preparing the respondent to communicate with their practitioner at a consultation focused on making a health decision. The eHealth Impact Questionnaire-Part 2 will be assessed and descriptive statistics will evaluate the impact of using the decision aid website across three domains: 1) confidence and identification of health concerns, 2) information and presentation of website material, and 3) understanding and motivation to manage health issues.

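### Sections 5.1 and 5.4 define different IPQ-R outcomes and 5.2 chooses neither; the item reversal that the IPQ-R and RCAC need for higher to mean worse is not written down

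*Combined protocol and SAP*

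**What the plan says.** **IPQ-R score.** Section 5.1 states "5 subscales will be used (5 to 6 items each; 28 items total" and then "Each subscale is scored separately, and averages are calculated"; it defines no total. Section 5.4, Outcome 3, defines only a total: "Total scores range from 28 to 140, with higher scores indicating worse outcomes". Section 5.2 says "Similar procedures will analyze changes in the IPQ-R, RCACS, PROMIS Self-Efficacy, and the IES-R as secondary outcomes, controlling for key covariates" and does not say which score is meant.

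**RCAC score.** Section 5.1 lists six subscales and says "Mean scores are calculated, ranging from 1 to 5", without saying whether the mean is overall or per subscale. Section 5.4, Outcome 4, gives an 18-to-90 total. Section 4.0 describes the RCAC as having 8 items; 5.1, 5.4 and Appendix I all have 18.

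**Direction and coding.** Section 4.0 describes the IPQ-R "with higher scores indicating worse outcomes", and 5.1 and 5.4 agree. The same direction is stated for the RCAC. Section 5.4 attaches 1 to strong disagreement and 5 to strong agreement for both scales. For the IPQ-R, 5.1 lists the anchors the other way round, from strong agreement to strong disagreement, against 4.0, 5.4 and Appendix H.

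**Items.** Appendices H and I contain items worded in both directions. Appendix H labels no subscales and notes that questions will be adapted for participants with confirmed infertility as opposed to risk. No reversal key appears in 4.0, 5.1, 5.2, 5.4 or either appendix.

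**The concern.** Objective 2 exists to produce preliminary effect sizes. For the IPQ-R, one total and five separate means are different outcomes, and a plan that defines both leaves the choice open until the data are in hand. The total is also hard to interpret. It pools control items, where agreement is mostly favourable, with consequence and emotion items, where it is mostly unfavourable. Section 2.0 frames the hypothesis in specific terms, "We hypothesize the web-based tool will help YA-Fs become informed, manage negative affect, and plan financially for future costs", and a pooled sum cannot show which of these moved.

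The second issue is coding. With items worded in both directions, no assignment of 1 and 5 to the anchors can by itself make higher mean worse; some items must be reversed. An analyst who followed 5.4 to the letter would compute a score that lacks the direction 5.4 claims for it.

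**Working it through.** **1. The plan's own ranges.** IPQ-R: 28 × 1 = 28 and 28 × 5 = 140. RCAC: 18 × 1 = 18 and 18 × 5 = 90. Both reproduce exactly, with or without reversal. The ranges are therefore correct, and the questions are which score is used and which way it points.

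**2. Total against subscale means.** Reading the item blocks from order and content in Appendix H (an inference, since none are labelled): Consequences 1–6, Personal control 7–12, Treatment control 13–17, Illness coherence 18–22, Emotional representations 23–28. Sizes are 6 + 6 + 5 + 5 + 6 = 28, matching the 5 to 6 items per subscale in 5.1. Item 22 reads like a control item, but moving it to Treatment control gives 6 + 6 + 6 + 4 + 6, which breaks that rule.

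With complete items, the total is 6 × Consequences + 6 × Personal control + 5 × Treatment control + 5 × Coherence + 6 × Emotional. Five means cannot be recovered from one sum. As an illustration with assumed, correctly keyed changes, −0.5 on Emotional (6 × −0.5 = −3) and +0.5 on Personal control (6 × 0.5 = +3) give a total change of 0.

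The RCAC differs. If the 5.1 mean is over all 18 items, it equals the total divided by 18 when every item is answered, and Cohen's d is unchanged.

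**3. Item direction, judged from wording.** Agreement is favourable on IPQ-R items 3, 7, 11, 14, 15, 16 and 26, with 8 and 9 arguable, and on RCAC items 5, 10 and 15. So k = 7 to 9 of n = 28, and k = 3 of n = 18.

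**4. Result if reversal were omitted under the 5.4 coding.** Best possible = 5k + (n − k). Worst possible = k + 5(n − k). Share kept of a change that is the same on every item = (n − 2k)/n.

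| Scale | k | Best | Worst | Share kept |
|---|---|---|---|---|
| IPQ-R, 8 and 9 favourable | 9 | 45 + 19 = 64 | 9 + 95 = 104 | 10/28 = 36% |
| IPQ-R, only 9 not favourable | 8 | 40 + 20 = 60 | 8 + 100 = 108 | 12/28 = 43% |
| IPQ-R, neither favourable | 7 | 35 + 21 = 56 | 7 + 105 = 112 | 14/28 = 50% |
| RCAC | 3 | 15 + 15 = 30 | 3 + 75 = 78 | 12/18 = 67% |

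**5. Non-uniform change.** The unreversed total would rise despite improvement if the average gain on favourably worded items exceeded (n − k)/k times the gain on the others: 19/9 = 2.1 times for the IPQ-R with k = 9, 21/7 = 3 times with k = 7, and 15/3 = 5 times for the RCAC. The sign is not guaranteed.

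**6. By subscale, same formula and the inferred map.** Consequences and Emotional representations: (6 − 2)/6 = 67%. Illness coherence: 100%. Treatment control: (5 − 6)/5 = −20%, or (6 − 6)/6 = 0 if item 22 belongs there. Personal control: (6 − 8)/6 = −33% with items 8 and 9 favourable, 0 with only 9 not favourable, and (6 − 4)/6 = +33% with neither. RCAC Acceptance (items 5, 10 and 15): (3 − 6)/3 = −100%, fully backwards. The key therefore matters most for the control and Acceptance subscales.

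**7. Anchor order.** If the 5.1 IPQ-R order were used as coding, with strong agreement = 1, the unreversed total at k = 9 would run from 19 × 5 + 9 × 1 = 104 (best) to 19 × 1 + 9 × 5 = 64 (worst), opposite to the stated direction.

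**The case against.** The strongest reply concerns the coding. Sections 4.0, 5.1 and 5.4 all say that higher is worse, which can hold only if favourably worded items are reversed. The instruments are described as validated and are cited. The appendices represent participant forms, where a scoring key would not be expected, and 5.4 may only be describing response options.

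Much of this stands. Reversal is the likely intent, and every figure in steps 4 to 7 is conditional on its omission. A reader might infer that the trial will report attenuated or inverted results; the documents do not support that. Nor do they support the opposite comfort, that unreversed totals would be diluted but keep their sign, which holds only when gains are spread evenly enough.

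The reply is not complete, however. The plan does not say that any external scoring rule applies, the IPQ-R items were adapted, and 5.1 and 5.4 give opposite anchor orders. For the DCS, whose items are all favourably worded, 5.4 sets strong agreement to 1, so the anchors alone give the right direction there. They cannot do so for scales worded both ways.

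It may also be said that the RCAC mean and total are equivalent. That is true if the mean is over all 18 items, and then the gap is only one of wording. Nothing in the reply settles the IPQ-R choice, because reversal does not decide between a total and five subscales.

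**Conclusion.** Wrong as written, for secondary outcomes only; the primary DCS is not touched. The firm part is the IPQ-R: 5.1 and 5.4 define different outcomes and 5.2 does not choose. This follows from the text and needs no assumption.

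The smaller part is the unwritten reversal. It rests on item directions read from wording, with items 8 and 9 left open, and on the 5.4 coding being followed literally. On that footing the IPQ-R total keeps 36% to 50% of a uniform change and the RCAC total 67%, with the RCAC Acceptance items running backwards.

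A reader might also infer that the printed score ranges are wrong, or that five IPQ-R tests call for a formal multiplicity rule. The ranges are exact. Objective 2 seeks preliminary effect sizes in a single-arm pilot, so it is enough to present the five results in that spirit.

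**What to change.** - In 5.2 and 5.4, replace the IPQ-R total with the five subscale means already defined in 5.1, and print the item-to-subscale map, stating where item 22 belongs.
- Use one anchor order, strongly disagree = 1 to strongly agree = 5, in 4.0, 5.1 and 5.4.
- State that favourably worded items are recoded as 6 minus the score so that higher means worse: IPQ-R items 3, 7, 11, 14, 15, 16 and 26, and RCAC items 5, 10 and 15. The sponsor should decide and state the direction of IPQ-R items 8 and 9.
- State the key for each IPQ-R version, including the one adapted for confirmed infertility. Its wording is not shown, so the same key cannot be presumed.
- Give one RCAC score definition in 5.1 and 5.4. The overall mean of the 18 keyed items fits the 5.1 range and, with complete items, leaves Cohen's d the same as for the total. Reconcile the 8 items in 4.0 with the 18 elsewhere.

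The cost is wording in 4.0, 5.1, 5.2 and 5.4, matching registry text and recoding syntax. Stored item responses can be rescored, so no new data are needed. The downside is that five IPQ-R results are reported instead of one, to be read as preliminary effect sizes.

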6.0 DATA MANAGEMENT CONSIDERATIONS

6.1 Data management

REDCap will be used to administer online surveys to collect data. SPSS will be used to analyze data.

6.2 Confidentiality

Describe procedures for protecting the privacy interests of participants, including the confidentiality of research records and biospecimens. Describe how study data are coded

and linked to participant identity in the study database (for example, is there a separate file with all identifying information or are data and identifiers kept together).

We will follow Stanford policies for maintaining and storing confidential data. All data files stored on computers, external hard disks, or USB thumbs (ie, any electronic devices that contain identifiable subject data) will be encrypted and password protected. Only the PI will have access to PHI data.

APPENDIX A: Participant Eligibility Checklist

A Participant Eligibility Checklist must be completed in its entirety for each subject prior to registration. The completed, signed, and dated checklist must be retained in the patient's study file and the study's Regulatory Binder.

The study coordinator, treating physician, and an independent reviewer must verify that the participant's eligibility is accurate, complete, and legible in source records. A description of the eligibility verification process should be included in the EPIC or other Electronic Medical Record progress note.

Protocol Title:	Pilot Study of a Decision Aid Intervention for Family-building After Cancer
Protocol Number:	IRB-52143
Principal Investigator:	[name]

II. Subject Information:

Subject Name/ID:
Gender:  Female

III. Study Information:

SRC-approved IRB-approved

IV. Inclusion/Exclusion Criteria

Inclusion Criteria (From IRB-approved protocol)	Yes	No	Supporting Documentation*
1. Female			Subject self-report
2. Age 18 to 45 years old			Chart review and/or subject self-report
3. Understands verbal and written English			Subject self-report
4. Completed cancer treatment known to have gonadotoxic effects (eg, systemic chemotherapy, surgery affecting reproductive organs or hormone regulation, and/or pelvic radiation)			Chart review and/or subject self-report
5. Desires future children or is uncertainty about family-building plans			Subject self-report
6. Access to the Internet and use of a computer, tablet, or smartphone			Subject self-report
Exclusion Criteria (From IRB-approved protocol)			
1. Currently undergoing cancer treatment excluding long-term adjuvant or maintenance therapies, such as tamoxifen			Chart review and/or subject self-report

2. Significant physical or mental disability that prevents completion of study activities			Subject self-report and/or screener's observation
---	--------------------------	--------------------------	---

